11.0 MANAGEMENT OF HIV ISSUES DURING AND FOLLOWING STUDY

11.1 HIV Testing

All volunteers will be tested for HIV as indicated in the Schedule of Procedures (Appendix A) or as needed, if medical or social circumstances arise. All volunteers will receive HIV risk reduction counselling and pre- and post-HIV-test counselling, as specified in Section 11.3.1 Counselling.

Volunteers who have a positive HIV serology test as a result of receipt of rAAV1-PG9DP and injection-induced HIV antibodies will have their test results reported as "Not infected with HIV-1 or HIV-2" (to prevent unblinding of volunteer and staff). A product recipient who still tests HIV positive due to injection-inducted antibodies at the end of the study will be informed of his/her positive test result and offered continuing follow-up until the test becomes negative.

If a volunteer is found to be HIV-infected through exposure to HIV in the community during the course of the study, the volunteer will be followed up as specified in Section 11.3.

Should a volunteer require an HIV test outside the study for personal reasons, it is recommended that the volunteer contact the study staff first. The HIV test should be done at the study site and then processed at an independent laboratory as above. Written evidence of HIV status (HIV-infected or HIV-uninfected) will be provided upon request.

11.2 Social Discrimination as a Result of a Seroreactive Diagnostic Test for HIV

To minimize the possibility of social discrimination in volunteers (if any) who test positive on a diagnostic HIV antibody test due to PG9 antibodies, appropriate diagnostic HIV testing and documentation/information will be provided both during and after the study as needed.

11.3 HIV infection

Volunteers who are found HIV infected at screening and volunteers who acquire HIV infection after screening, during the study (intercurrent HIV-infection) will be provided the following:

11.3.1 Counselling

The volunteer will be counselled by appropriately trained study investigational staff. The counselling process will assist the volunteer with the following issues:

- Psychological and social implications of HIV infection
- Whom to inform and what to say
- Implications for sexual partners
- Avoidance of transmission to others in future

11.3.2 Referral for Support/Care and Long Term Follow-Up Protocol for HIV Infection

Volunteers will be referred to a patient support centre or institution of his/her choice for a full discussion of the clinical aspects of HIV infection. Referral will be made to a designated physician or centre for discussion of options of treatment of HIV-infection.

For those individuals who become HIV infected after enrolment in the study (i.e., from injection through final study visit), antiretroviral therapy will be provided when clinically indicated according to accepted treatment guidelines.

12.0 DEFERRAL OF INJECTION AND/OR WITHDRAWAL FROM STUDY

12.1 Deferral of Injection

Injection may be temporarily deferred if the volunteer is clinically ill at the time of the injection visit and/or presents with fever at the time of the injection visit. A volunteer must be clinically well and afebrile for a minimum of a 24-hour consecutive period prior to injection.

12.2 Withdrawal from the Study (Early Termination)

Volunteers may be withdrawn from the study permanently for the following reasons:

- 1. Volunteers may withdraw from the study at any time if they wish, for any reason
- 2. The Principal Investigator or designee has reason to believe that the volunteer is not complying with the protocol
- 3. If the Sponsor decides to terminate or suspend the study
- 4. If a volunteer becomes infected with HIV (through exposure in the community)

If a volunteer withdraws or is withdrawn from the study, all termination visit procedures will be performed according to the Schedule of Procedures (Appendix A) when possible. Every effort will be made to determine and document the reason for withdrawal.

13.0 DATA HANDLING

13.1 Data Collection and Record Keeping at the Study Site

Data Collection: All study data will be collected by the clinical study staff using designated source documents and entered onto the appropriate case report forms (CRFs). CRFs will be provided by IAVI and should be handled in accordance with the instructions from IAVI. All study data must be verifiable to the source documentation. A file will be held for each volunteer at the clinic(s) containing all the source documents. Source documentation will be available for review to ensure that the collected data are consistent with the CRFs.

All CRFs and laboratory reports will be reviewed by the clinical team, who will ensure that they are accurate and complete.

Source documents and other supporting documents will be kept in a secure location. Standard GCP practices will be followed to ensure accurate, reliable and consistent data collection.

Source documents include but are not limited to:

- Signed Informed Consent Documents
- Progress notes
- Data collection forms
- Documentation of any existing conditions or past conditions relevant to eligibility

- Printed laboratory results
- Print out of the IDES generated enrolment confirmation
- All Adverse Events
- Concomitant medications
- Local and systemic reactogenicity events

13.2 Data Collection and Transfer at the Human Immunology Laboratory

Data generated at the IAVI Human Immunology Laboratory will be transferred directly to the Data Coordinating Centre.

13.3 Data Entry at the Study Site

The data collected at the site will be recorded onto the CRFs by the study staff and entered into a database. To provide for real time assessment of safety, data should be entered as soon as reasonably feasible after a visit occurs.

13.4 Data Analysis

The data analysis plan will be developed and agreed upon by the Sponsor, PI and IMP Developer prior to unblinding of the study. The statistician at the Data Coordinating Centre (DCC) in collaboration with the Principal Investigator, Sponsor and Developer of AAV-PG9DP will create tables according to this data analysis plan.

The DCC will conduct the data analysis and will provide interim and final study reports for the Sponsor, Principal Investigator, the SRB and the regulatory authorities, as appropriate.

14.0 STATISTICAL CONSIDERATIONS

14.1 Sample Size

The total number enrolled will depend on the course of dose escalation. Up to 24 total volunteers (18 active, 6 placebo) may be enrolled.

14.2 Statistical Power and Analysis

Safety and Tolerability:

The frequency of local and systemic reactogenicity events will be determined and compared between IMP regimens.

The frequency of SAEs judged possibly, probably or definitely related to the IMP will be determined. AEs that may be temporarily incapacitating (for example, loss or cancellation of work or social activities), which could make an IMP impractical for large scale use if they occur in more than a small proportion of cases, will also be described.

All AEs will be analysed and, grouped by seriousness, severity and relationship to the IMP (as judged by the investigator).

For specific adverse events related to the IMP: if none of the volunteers receiving the IMP experience such reactions, then the 95% upper confidence bound for the rate of

these adverse events in the population is 26.5%, 21.8% and 18.5%, depending on whether the total number of enrolled volunteers is 12 (Groups A, B, C, D), 15 (Groups A, B, C, D, D1) or 18 (Groups A, B, C, C1), respectively. If we consider a single dose group with only 3 volunteers receiving the IMP, then the 95% upper confidence bound for the rate of these adverse events in the population is 70.8%. All calculations are based on exact (Clopper-Pearson) confidence limits.

There is limited power for comparing the combined event rates between placebo and treatment arms. If all volunteers receiving the IMP are combined into a single group and compared with all placebo recipients, then the table below shows the difference (%) in event rates, depending on the final sample size, that will be detectable with 80% power at alpha levels of 0.05 and 0.10 using Fisher's exact 1-tailed test (assuming that event rates are lower in the placebo group). At the 5% level of significance the minimum detectable difference is 70% and at the 10% level of significance it is 47%. All calculations were made using PASS 2008 (Version 08.0.6).

Detectable difference (%) in event rates that will be detectable with 80% power at alpha levels of 0.05 and 0.10 using Fisher's exact 1-tailed test

	Sample size	ze True event rate in the placebo group									
Alpha	Vaccine/Placebo	0.01	0.05	0.10	0.15	0.2	0.25				
0.05	15/5	67%	68%	70%	70%	69%	67%				
	18/6	57%	59%	60%	62%	62%	61%				
0.10	15/5	54%	56%	58%	59%	60%	60%				
	18/6	47%	51%	55%	56%	57%	56%				

Considering the low power available for group comparison and the associated risk of false safety signal in the context of multiple exploratory analyses, the analysis of safety events will be based on within-group descriptive summaries for the incidence rate of each event. The associated 95% confidence intervals for the incidence rate within each group will also be provided.

Immunogenicity:

Cellular immune response rates (including ELISPOT and ICS), PG9 titres and neutralizing antibody response rates will be reported and analyzed using binomial methods. Descriptive statistics of the magnitude of response (ELISPOT and ICS counts, PG9 titres and neutralizing antibody titres) will also be provided, including mean, standard deviation and median, as well as the geometric mean titre (GMT) and corresponding 95% confidence interval. The breadth of neutralizing antibody responses to the various viruses will also be summarised (frequencies and proportions). Due to the small sample sizes per group, these analyses will be mainly descriptive. Assays will be performed using the IAVI HIL and trials site SOPs and standard reagents for all volunteers.

Based on the previous experience with IAVI Phase 1/2 IMP studies, it is expected that the amount of missing, unused or spurious data will be insignificant. Unused and

spurious data will be listed separately and excluded from the statistical analysis. Missing data will be excluded from the statistical analysis.

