- If safety criteria to allow dose escalation are met and PG9 antibody expression is sufficient (~150ug/ml), the study will proceed to enrol an expanded number of volunteers at the Group C dose (Group C1) and enrolment into Group D will not occur.
- Otherwise, if PG9 antibody expression is not sufficient but safety criteria for dose escalation are met, the study will proceed to enrol the highest dose level (Group D). Safety and tolerability will be evaluated by the SRB over at least 56 days for volunteers in Group D. Once safety data through Day 56 post-injection visit is available for all volunteers in Group D, all available safety data (Groups A, B, C and D) will be reviewed by the SRB. If criteria for dose escalation are met, the study will proceed to enrol an expanded number of volunteers at the Group D dose (Group D1).

In the study all groups will be randomized in a 3:1 ratio of active product to placebo with the exception of Group D1, where 5 volunteers will be randomized in a 4:1 ratio of active product to placebo.

Table 5.0-1 Study Design

	Number Active/						
Group	Placebo	Dose (vg)	Route	Month 0			
А	3/1	4x10 ¹² or Placebo	IM	х			
SRB revie	SRB review						
в	3/1	4x10 ¹³ or Placebo	IM	х			
SRB review							
с	3/1	8x10 ¹³ or Placebo	ІМ	x			
SRB review to determine progression to either C1, or D and D1							
C1	9/3	8x10 ¹³ or Placebo	IM	х			
Total Number of Volunteers: 24 (18/6)							
OR							
D	3/1	1.2x10 ¹⁴ or Placebo	IM	Х			
SRB review							
D1	4/1	1.2x10 ¹⁴ or Placebo	IM	Х			
Total Number of Volunteers: 21 (16/5)							

IM=Intramuscular

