Note: This summary reflects changes between approved protocol IAVI A003/ CHOP HVDDT 001 v4.0 07 Oct 2014 and amendment version 6.0 12 Apr 2016. Formatting, minor grammar and word choice changes or clarifications are not indicated. Changes are noted in track changes.

1.	Section Number & Title:	Synor	Synopsis: Study Design Table, and Table 5.0-1: Study Desig					
	Previous Text:		Group	Number Active/ Placebo	Dose (vg)	Route	Month 0	
			А	3/1	4x10 ¹² or Placebo	IM	x	
			SRB review					
			в	3/1	4x10 ¹³ or Placebo	IM	x	
			SRB review					

		1	ir	1			
	с	3/1	8x10 ¹³ or Placebo	IM	х		
	SRB revi and D1	SRB review to determine progression to either C1, or D and D1					
	C1	9/3	8x10 ¹³ or Placebo	IM	x		
	Total Nu	mber of Vo	lunteers: 24	(18/6)			
			OR				
	D	3/1	1.2x10 ¹⁴ or Placebo	IM	X		
	SRB revi	ew					
	D1	3/1	1.2x10 ¹⁴ or Placebo	IM	X		
	Total Nu	mber of Vo	lunteers: 20	(15/5)			
Revised Text:		Number					
	Group	Active/ Placebo	Dose (vg)	Route	Month 0		
	A	3/1	4x10 ¹² or Placebo	IM	X		
	SRB revi	SRB review					
	в	3/1	4x10 ¹³ or Placebo	IM	x		
	SRB revi	ew					
	с	3/1	8x10 ¹³ or Placebo	IM	x		
	SRB revi and D1	SRB review to determine progression to either C1 , or D and D1					
	C1	9/3	8x10 ¹³ or Placebo	IM	х		
	Total Nu	mber of Vo	lunteers: 24	(18/6)			
			OR				
	D	3/1	1.2x10 ¹⁴ or Placebo	IM	X		
SRB review							
	D1	4/1	1.2x10 ¹⁴ or Placebo	IM	X		
	TIGAN	weber of Ve	lunteers: 21				

Rationale:	The number of volunteers to be enrolled in Group D1 has changed from 4 to 5. 4 volunteers will be randomized to receive active IMP and 1 volunteer will be randomized to receive placebo.
	Adding one volunteer would allow us to collect the maximum amount of data in this small phase I study, since there are enough vials of active IMP remaining for a fifth volunteer to be enrolled in the high-dose group.
Impact on other study documents:	Updates are required in the site-specific informed consent documents (ICDs.) The revised ICDs will be submitted to ethics and regulatory committees per local guidelines. The study operations manual and lab analytical plans will be updated as well.

2.	Section Number & Title:	Synopsis: Study Population

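### Section 14.2 still computes the A–D1 path for 15 active / 5 placebo although the design is now 16/5; a small correction to one bound, two table rows and two sentences

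*Protocol*

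**What the plan says.** Section 5.0 gives a 3:1 ratio to every group except Group D1, "where 5 volunteers will be randomized in a 4:1 ratio of active product to placebo". Table 5.0-1 and the synopsis design table both close the A–D1 path with "Total Number of Volunteers: 21 (16/5" in parentheses, that is, 16 active and 5 placebo.

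Section 14.2 says that if no product recipient has a given related event, the upper bound for the rate of "these adverse events in the population is 26.5%, 21.8% and 18.5" percent. These three values belong in turn to 12 (Groups A to D), "15 (Groups A, B, C, D, D1) or 18 (Groups A, B, C, C1), respectively". The text describes 12, 15 and 18 as counts of enrolled volunteers. It adds a bound of 70.8% for a single group of 3 recipients and says "All calculations are based on exact (Clopper-Pearson) confidence limits".

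A table then gives differences "detectable with 80% power at alpha levels of 0.05 and 0.10 using Fisher's exact 1-tailed test", for 15/5 and for 18/6. The sentence before it gives 70% as the minimum detectable difference at the 5% level and 47% at the 10% level.

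**The concern.** Section 14.2 contradicts the design table on how many people receive product along one of the two permitted expansion paths. Both statements are current text. The version 6.0 summary of changes only explains the origin: "The number of volunteers to be enrolled in Group D1 has changed from 4 to 5", which took the path from 20 (15/5) to 21 (16/5). None of the 19 items in that summary touches Section 14.

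These are the Protocol's only statements of precision and power. A reader who quotes them for the A–D1 path would quote figures for a different sample size. The same paragraph has two further slips that must be settled in the same edit: recipients of product are called enrolled volunteers, and the 70% sentence does not agree with its own table.

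**Working it through.** **Counts.** From Table 5.0-1:
- A–D: active 3+3+3+3 = 12, placebo 4, enrolled 16.
- A–D1: active 12+4 = 16, placebo 5, enrolled 21.
- A–C1: active 3+3+3+9 = 18, placebo 6, enrolled 24.

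No planned stopping place gives 15/5. The numbers 12 and 18 in Section 14.2 are active counts, not enrolled totals.

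**Zero-event bound.** The upper Clopper–Pearson limit of a two-sided 95% interval for 0/n is 1 − 0.025^(1/n).
- Printed values reproduced: n=3, 70.8%; n=12, 26.5%; n=15, 21.8%; n=18, 18.5%.
- Current design: n=16, 1 − 0.025^(1/16) = 20.6%, a change of 1.2 points.

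**Detectable difference.** For each pair of event counts (x active, y placebo), the one-tailed Fisher p-value is the hypergeometric probability of x or more active events given x+y in total. Power is the sum of the two binomial probabilities over all pairs with p ≤ alpha. The detectable difference is the smallest one with power of at least 80%, in steps of 0.1 point.

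The method reproduces the printed rows for 15/5 and 18/6 to within about half a point. For the A–D1 path (all in %):

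| Placebo rate | 1 | 5 | 10 | 15 | 20 | 25 |
|---|---|---|---|---|---|---|
| α 0.05, printed 15/5 | 67 | 68 | 70 | 70 | 69 | 67 |
| α 0.05, recomputed 15/5 | 67.1 | 68.5 | 69.8 | 69.6 | 68.6 | 67.3 |
| α 0.05, 16/5 | 63.4 | 64.6 | 65.9 | 66.8 | 67.2 | 66.1 |
| α 0.10, printed 15/5 | 54 | 56 | 58 | 59 | 60 | 60 |
| α 0.10, recomputed 15/5 | 54.5 | 56.1 | 58.0 | 59.4 | 60.4 | 60.5 |
| α 0.10, 16/5 | 51.8 | 55.3 | 59.3 | 60.9 | 61.6 | 61.4 |

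At the printed 15/5 differences, a 16/5 trial has power 0.82 to 0.87 at alpha 0.05 and 0.77 to 0.84 at alpha 0.10.

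**Why some alpha 0.10 cells rise.** The test is discrete. With one placebo event, 10 of 15 active events give p = (3003×5 + 1365)/167960 = 0.098, which is significant. With 16 active, 10 events give (8008×5 + 4368)/352716 = 0.126, so 11 are needed. The extra volunteer raises the hurdle as well as the information.

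**The 70% sentence.** At the 5% level the printed entries run from 57% (18/6, placebo rate 1%) to 70% (15/5, placebo rates 10% and 15%). So 70% is the largest entry, while the 47% given for the 10% level is the smallest entry at that level. Once the 15/5 row is replaced, the largest 5% entry is 67% and 70% matches no cell.

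**The case against.** The strongest reply is that nothing turns on these figures. Section 14.2 itself concedes limited power and bases the safety analysis on within-group descriptive summaries. Escalation (Section 17.2.2) and pausing (Section 17.4) are triggered by events. The fifth D1 volunteer was added because vials of product remained, not for power. The printed bound and all six alpha 0.05 entries err on the cautious side. All of this stands, and it sets the weight of the point. It does not make the text right, and caution is not uniform: four alpha 0.10 entries are 1 to 2 points too small.

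A reader might infer more than the documents support:
- *That the calculations are faulty.* They are not; each bound and table row follows from its stated input.
- *That 15/5 can never arise.* It matches no planned total, but under-enrolment or the loss of one active volunteer could produce it.
- *That calling these limits 95% upper bounds is an error because they come from two-sided intervals.* Section 14.2 names Clopper–Pearson limits, and the upper limit of a two-sided 95% interval fits that description and is the more cautious choice.
- *That the pooled bound overstates what will be known at the top dose.* Section 14.2 lists the groups it pools, gives the single-group value for n=3, and promises within-group intervals. A limit for the 7 recipients of D and D1 together (1 − 0.025^(1/7) = 41.0%) could be added, but the two groups differ in muscle and number of injections, and leaving it out is not a mistake.

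**Conclusion.** The inconsistency is real and confined to the A–D1 path: one bound and 12 table entries are computed for 15/5 when the design is 16/5. The bound moves by 1.2 points and the table entries by about 1 to 4 points. The bounds for n=3, 12 and 18 and both 18/6 rows stand. The description of 12, 15 and 18 as enrolled volunteers and the 70% sentence are also wrong as written.

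This is a minor correction, because no trial decision depends on the numbers. The 16/5 values assume full planned enrolment and the Protocol's own test, alpha levels, power and pooling of all active against all placebo recipients. They are rounded to whole points as in the printed table, so power at a rounded entry can fall slightly below 80%, as it does for some printed entries.

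**What to change.** In Section 14.2:
- Replace 15 with 16 and 21.8% with 20.6% for the A–D1 path.
- Replace the two 15/5 rows with 16/5 rows. For placebo rates 1, 5, 10, 15, 20 and 25%: alpha 0.05, 63, 65, 66, 67, 67, 66%; alpha 0.10, 52, 55, 59, 61, 62, 61%.
- Describe 12, 16 and 18 as numbers of volunteers receiving product; the enrolled totals are 16, 21 and 24.
- In the sentence on the minimum detectable difference, replace 70% with 57% for the 5% level and say that it comes from the 18/6 row at a placebo rate of 1%. The 47% for the 10% level stays and comes from the same place.

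The cost is one text and table edit. Enrolment, conduct and the planned analysis do not change.

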15.0 QUALITY CONTROL AND QUALITY ASSURANCE

To ensure the quality and reliability of the data collected and generated and the ethical conduct of this study, a Study Operations Manual (SOM) will be developed. All deviations will be reported and investigated. The SOM describes reporting and deviation documentation requirements and procedures.

Regular study monitoring will be performed according to ICH-GCP as indicated in Section 17.5.

An independent audit of the study and study site may be performed by the Sponsor or designee to establish the status of applicable quality systems. Inspection by regulatory authorities may also occur.

By signing the protocol, the Principal Investigator agrees to facilitate study related monitoring, audits, IRB/IEC review and regulatory inspection(s) and direct access to source documents. Such information will be treated as strictly confidential and under no circumstances be made publicly available.

16.0 DATA AND BIOLOGICAL MATERIAL

All data and biological material collected through the study shall be managed in accordance with the Clinical Trial Agreement (CTA). Distribution and use of these data will be conducted by agreement of all parties.

The computerized raw data generated will be held by the DCC on behalf of the Sponsor. The study site will also hold the final data files and tables generated for the purpose of analysis. Principal investigators or designees will have access to the clinical study database with appropriate blinding.

17.0 ADMINISTRATIVE STRUCTURE

The Principal Investigator will be responsible for all aspects of the study at the study site.

17.1 Protocol Safety Review Team (PSRT)

A PSRT will be formed to monitor the clinical safety data. Until 6 weeks after the last volunteer is injected, the PSRT will review the clinical safety data on a weekly basis via electronic distribution of reports. An ad hoc PSRT review meeting will occur if any of the members of the PSRT requests a special review to discuss a specific safety issue or as specified in the Study Operations Manual. After the injection phase the PSRT will review the clinical safety data at least monthly.

The PSRT will consist of the IAVI Medical Monitor(s) and PI or designee from the clinical team. The study chair or an IAVI Medical Monitor may be the PSRT chair. *Ex officio*

members will include the IAVI Chief Medical Officer, IAVI Medical Monitor and representatives from the IMP Developer.

Additional PSRT participants may include the following, as needed:

- Co-investigators and trial site senior clinical research nursing staff
- Laboratory directors
- Data management, study statistician and regulatory staff

The PSRT membership and procedures are detailed in the PSRT charter.

